1.3.10 Data management and confidentiality

Standard institutional practices will be followed as described in the OHSU Information Security and Research Data Resource Guide (http://ozone.ohsu.edu/cc/sec/isq/res_sec.pdf) to maintain the confidentiality and security of data collected in this study. Study staff will be trained with regard to these procedures.

Upon enrollment, subjects will be assigned a code that will be used instead of their name, medical record number or other personally identifying information. Electronic files for data analysis will contain only the subject code. Codes will not contain any part of the 18 HIPAA identifiers (initials, DOB, MRN). The key associating the codes and the subjects personally identifying information will be restricted to the PI and study staff. The key will be kept secure on a restricted OHSU network WHRU drive in a limited access folder. Electronic data will be maintained on the secured WHRU OHSU computer server utilizing only subject IDs without personal identifying information, or in a web-accessible REDCap database housed on an OHSU secure server. No patient names will be included with any study data records or during statistical analysis. Paper files will be stored in locked filing cabinets in restricted WHRU offices at OHSU.

Subject phone numbers, email addresses and study ID numbers will be entered into the OHSU/Mir3 message system solely for the purpose of sending and receiving bleeding diary text or email messages. No additional identifying information will be entered into this system. Mir3 works with some of the largest banks, healthcare institutions, universities and government institutions and follows a strict privacy policy to ensure that each customer's data, including phone numbers, are kept private and encrypted. Any data transmitted via the Mir3 system is encrypted according to advanced standards. No subject information will be retained by Mir3 after each subject completes the project.

All telephone screenings and website submission forms will be stored in a locked office at OHSU, with access limited to study staff. For subjects electing to enroll in the study, this

information will become a part of their protected research record. For subjects choosing not to enroll or who screen fail, all PHI will be stored confidentially with the research study information in a locked cabinet and archived with other study-specific documents at the close of the trial. All potential participants that contact the department for research studies will be added to a password-protected log listing their contact information, only accessible through OHSU password-protected computers by study staff. Phone screens (including for individuals who choose not to participate or are ineligible) and the log containing potential participants' information are saved to ensure that our department has a record of contact with the participant and to monitor our recruitment outreach efforts. Confidentiality of personal health information will be maintained according to HIPAA requirements for research and all data will be kept in locked files or in a password-protected document on a password protected computer. Once the study is complete and all data analysis and publication has been completed, the study information is stored indefinitely in a secure manner that follows OHSU Standard Institutional practices and all FDA and HIPAA guidelines.

1.3.11 Data analysis

Data will be extracted and entered into STATA on a password-protected computer. Analysis will be performed with the blinded data. P value of 0.05 defines statistical significance. Randomization will be assessed and if there is imbalance found between treatment and placebo groups, regression analyses will be completed to accommodate these differences.

Primary objectives: The primary measurement for this study will be the mean number of bleeding or spotting (b/s) days experienced by participants in the treatment group compared to placebo group over 30 days after treatment initiation. We will record baseline data on b/s days in the 21-day run-in period to confirm that the randomization was successful in allotting women with equivalent baseline b/s days to each group. Each day, subjects will indicate via numeric coded text or email message response whether they had spotting, bleeding, or none. From these diaries, counts of total bleeding/spotting days will be obtained. Other secondary bleeding outcomes will be examined including number of bleeding/spotting episodes, the number of prolonged bleeding episodes (>8 days), and the longest bleeding-free interval. Comparisons between groups will be made using an independent sample two sided t-test. Data will be analyzed in an intention-to-treat fashion. If data are very skewed, non-parametric methods will be used to compare groups.

Secondary objectives:

1. Satisfaction and side effects

At the study visit and in the final survey, subjects will answer questions regarding their satisfaction with the IUS and their bleeding patterns, acceptability of bleeding, as well as side effects and adverse events. Satisfaction responses will be quantified using a visual analog scale between 0-100mm. Discontinuation from the study and discontinuation of the IUS during the study will be monitored as markers of dissatisfaction. Comparison of means between tamoxifen and placebo groups will be made using two sided t-tests, and side effects will be reported descriptively.

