1.1.2 Objectives and hypotheses

Hypothesis: Users of the LNG-IUS who receive tamoxifen 21 days after insertion of their device will have a reduction in bleeding/spotting days over the next 30 days compared to placebo.

Primary objective: To determine whether tamoxifen taken preventively in users of the LNG-IUS can reduce the total number of bleeding/spotting days by 40% over 30 days compared to placebo.

Secondary objectives: To determine whether tamoxifen:

1. Leads to a longer duration of bleeding-free days after dosing than placebo
2. Improves satisfaction with the LNG-IUS
 - a. Visual analog scale; anchors 0 = not at all satisfied, 100mm = very satisfied
 - i. With bleeding pattern

- ii. With LNG-IUS overall as a method of contraception
- 3. Improves continuation of the LNG-IUS
 - a. Track discontinuation of the device during the study
- 4. Causes side effects
 - a. Track self-reported adverse events (AEs) and severe adverse events (SAEs)

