Women who enroll in the study will track bleeding and spotting starting on the day after LNG-IUS insertion via response to daily automated text messages. Those who are compliant with text message diaries over the first 14 days (responding 12 or more days, approximately 90% response rate) will be invited by phone to return for study visit 1 (occurring between 14-21 days after IUS insertion). On this scheduling phone call, post-insertion exclusions will be reviewed. Eligible women scheduled for study visit 1 will be randomized by the OHSU research pharmacy on the day prior to their scheduled visit. We anticipate that ensuring compliance with preliminary data collection will help minimize loss to follow up or missing data after randomization. The baseline bleeding data may be used as a covariate in final analysis.

The OHSU research pharmacy will randomize subjects to tamoxifen or placebo through a computer-generated algorithm using a block size of six. Treatment allocation will be double-blinded and study investigators will not have access to the randomization scheme or treatment assignments. The research pharmacy will maintain allocation concealment until completion of the study. Study drug (oral tamoxifen 10mg) will be purchased and routed through the OHSU research pharmacy, and identical placebo will be compounded by the research pharmacy. At

study visit 1, each subject will receive a total of seven days of medication to take home (14 pills). They will be instructed to start this medication on day 21 after insertion of their LNG-IUS.

Women with inadequate responses to the text message diary (less than 12 of 14 days) during the 14-day observation period will be contacted by phone to confirm discontinuation from the study, and they will stop receiving automated text messages.

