Between IUS insertion and study visit 1 (occurring 14-21 days after insertion), baseline bleeding with the LNG-IUS will be prospectively collected using bleeding diaries. This data will be used later as a covariate in analysis. A co-investigator (ob/gyn physician) will call each subject after at least 12 days of bleeding data collection to review exclusion criteria and to schedule study visit 1 if appropriate, as described in section 1.3.4. Subjects reporting concerns with their IUS will be referred to their primary provider or scheduled for a triage visit in family planning clinic to be examined by a physician as clinically indicated.

At study visit 1, bleeding diaries will be reviewed, and VAS scales (0-100mm) will be completed to obtain baseline assessment of bleeding satisfaction with the LNG-IUS. Each subject will receive one bottle of their assigned medication. Participants will be instructed to begin use of the study medication on day 21 after the insertion of their LNG-IUS and continue to take a twice daily oral dose of 10 mg for seven days. Estimated time to complete this visit is 15 minutes. Participants will receive a single text message or email reminder on the day they are due to start study medication. There will not be any specimens collected at this visit and there will be no results to share with subjects.

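### The plan gives the pre-dose satisfaction VAS no role in comparing satisfaction between arms; a pre-specified ANCOVA would usually gain precision at almost no cost

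*Combined protocol and SAP*

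**What the plan says.** Section 1.1.2 lists satisfaction as a secondary objective with two VAS items: one on the bleeding pattern and one described as "With LNG-IUS overall as a method of contraception".

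- **Collection.** Section 1.3.6 says that at study visit 1 "VAS scales (0-100mm) will be completed to obtain baseline assessment of bleeding satisfaction with the LNG-IUS". Section 1.3.7 repeats the satisfaction VAS electronically in the online survey 30 days after study drug is started. Section 1.3.11 describes both time points: "At the study visit and in the final survey, subjects will answer questions regarding their satisfaction with the IUS and their bleeding patterns".
- **Analysis.** For these scores section 1.3.11 states: "Comparison of means between tamoxifen and placebo groups will be made using two sided t-tests, and side effects will be reported descriptively". The variable to be tested (final score or change) is not named.
- **Adjustment.** The only adjustment rule in section 1.3.11 is conditional: "if there is imbalance found between treatment and placebo groups, regression analyses will be completed to accommodate these differences". It names no variables and no criterion for imbalance.
- **Covariates.** Section 1.3.4 says "The baseline bleeding data may be used as a covariate in final analysis" and section 1.3.6 says "This data will be used later as a covariate in analysis". Both sentences refer to the run-in bleeding diaries, not to the VAS.
- **Timing.** Section 1.3.4 says "Eligible women scheduled for study visit 1 will be randomized by the OHSU research pharmacy on the day prior to their scheduled visit". Study drug starts on day 21 after insertion, and visit 1 falls on days 14 to 21.

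**The concern.** The trial collects a baseline for satisfaction and gives it no place in the analysis. Three analyses fit the present text: a t-test on the final score, a t-test on the change, and a regression if someone judges the arms to be imbalanced. They differ in precision, sometimes by a lot, and nothing fixes the choice before the data are seen.

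With about 17 evaluable women per arm, only large differences in satisfaction can be detected. That makes a good predictor which is already collected worth using.

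There is also a small inconsistency. Section 1.3.6 names only bleeding satisfaction at visit 1, while section 1.3.11 implies that both items are asked there. If the overall LNG-IUS item is not on the visit 1 form, it has no baseline to adjust for.

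**Working it through.** **Inputs from the documents.** 42 women, 21 per arm, 20% dropout (section 1.3.2); two-sided tests at 0.05 (section 1.3.11).

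**Assumptions.** The correlation r between visit 1 and final VAS, the VAS SD, equal SDs at the two times, and approximate normality. None is given in the documents.

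**The plan's own sample size.** It rests on the primary outcome (7 days, SD 7, 80% power). The t-based requirement is 16.71, so 17 per arm; 17 × 1.2 = 20.4, rounded up to 21 per arm, which gives 42. The stated figure reproduces. No sample size or power is given for the VAS.

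**Evaluable women.** 21 × 0.8 = 16.8, taken as n = 17 per arm.

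**Is the visit 1 VAS a valid covariate?** It is recorded about a day after randomization, but allocation is blinded and the visit is when the drug is handed out for a day 21 start. Treatment cannot have affected it, so adjusting for it introduces no bias.

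**Variance of the treatment difference, relative to a final-score t-test (= 1):**

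- Change score: 2(1 − r), with 2n − 2 = 32 df.
- ANCOVA: (1 − r²) × (1 + 1/(2n − 4)) = (1 − r²) × (1 + 1/30), with 2n − 3 = 31 df. The second factor is the expected cost of estimating the slope.

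The detectable difference at 80% power comes from the noncentral t distribution:

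| Assumed r | ANCOVA variance factor | Final score (SD) | Change score (SD) | ANCOVA (SD) |
|---|---|---|---|---|
| 0 | 1.033 | 0.99 | 1.40 | 1.01 |
| 0.3 | 0.940 | 0.99 | 1.17 | 0.96 |
| 0.5 | 0.775 | 0.99 | 0.99 | 0.87 |
| 0.7 | 0.527 | 0.99 | 0.77 | 0.72 |

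**Break-even.** The ANCOVA variance factor falls below 1 once r exceeds √(1 − 30/31) = 0.18. Counting the lost degree of freedom as well, the detectable difference breaks even at r of about 0.19. At r = 0, power for a 0.99 SD effect falls from 80% to 79%.

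**Equivalent sample size.** At r = 0.5, 1/0.775 = 1.29, like 29% more women. At r = 0.3, 1/0.940 = 1.06, about 6% more.

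**In millimetres, with an assumed SD of 25 mm (95% CI half-width):**

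- t-test: 2.037 × 25 × √(2/17) = 17.5 mm
- ANCOVA, r = 0.3: 2.040 × 25 × √(0.940 × 2/17) = 17.0 mm
- ANCOVA, r = 0.5: 2.040 × 25 × √(0.775 × 2/17) = 15.4 mm

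**Does the imbalance-triggered regression fill the gap?** Section 1.3.11 gives no trigger, so two were assumed: adjust only if the baseline difference has p < 0.05, or p < 0.20. Simulated power (100,000 trials, true effect 0.991 SD):

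| Assumed r | t-test | Adjust if p < 0.05 | Adjust if p < 0.20 | Always adjust |
|---|---|---|---|---|
| 0.3 | 80.1% | 80.1% | 80.5% | 82.4% |
| 0.5 | 80.0% | 80.8% | 82.6% | 88.8% |
| 0.7 | 80.3% | 81.9% | 85.8% | 97.1% |

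Type I error at r = 0.5 is 5.0%, 4.5%, 3.9% and 5.1% in the same order. The triggered rules are conservative and recover little of the gain.

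**Effect of the open choice.** If the smallest p-value among final score, change score and ANCOVA were reported, the false-positive rate at r = 0.5 would be about 9.5% instead of 5% (simulation under no effect, 17 per arm).

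**The case against.** The strongest reply is that this replaces one valid test with a more efficient one, on a secondary outcome for which the plan makes no power claim. That is true and limits the weight of the point.

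The gain also depends on an unknown r, which may be modest. The two readings are about 30 to 37 days apart, bleeding is changing over that time, and the final VAS is electronic while the mode at visit 1 is not stated. At r = 0.2 the half-width is essentially unchanged (17.4 against 17.5 mm). This stands as a limit on the benefit, but the loss if r is low is about one point of power.

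Section 1.3.11 says the analysis is done on blinded data, which restricts choosing a method because it favours tamoxifen. It does not settle which method will be used, and nothing suggests the investigators intend to choose selectively.

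The trigger thresholds are assumptions, so the simulation describes plausible readings of the rule, not the rule itself. More than 17 per arm may also provide a final VAS, because section 1.3.9 asks women who discontinue the device to complete the survey before removal. At 21 per arm the t-test detects 0.89 SD, and ANCOVA at r = 0.5 detects 0.78 SD, so the comparison is unchanged.

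Finally, a bounded VAS may be skewed in a sample this small. The non-parametric fallback in section 1.3.11 should therefore be carried over to the adjusted analysis.

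**Conclusion.** The concern holds as a minor, worthwhile improvement. The plan leaves the role of the visit 1 VAS unstated. The covariate sentences elsewhere concern bleeding data, and the imbalance rule neither names the VAS nor recovers most of the available precision.

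The benefit ranges from almost nothing at r near 0.2 to a cut of about 22% in variance at r = 0.5 and 47% at r = 0.7. All of these rest on an assumed correlation, approximate normality and 17 evaluable women per arm. The t-test remains unbiased, and the primary analysis is not affected.

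**What to change.** In section 1.3.11, pre-specify for each satisfaction item (bleeding pattern; LNG-IUS overall) an ANCOVA of the final VAS on treatment arm plus the matching visit 1 VAS, done whether or not the arms look imbalanced. Report the adjusted difference with its 95% CI. State in the same place what replaces this model if the scores are very skewed, for example the same ANCOVA on ranks.

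In section 1.3.6, state that both VAS items are completed at visit 1.

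For bleeding satisfaction the cost is wording only, since its baseline is already collected. If the overall LNG-IUS item is not on the visit 1 form, one VAS line must be added. No extra visits or participants are needed.

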1.3.12 Study limitations

Medication dosing: The only prior published study to evaluate tamoxifen for this indication utilized 20mg daily (split dosing) for 10 days. However, the differences in bleeding patterns were detected within 3-7 days of starting medication; 82% of tamoxifen users stopped bleeding

within 7 days, compared to 56% of placebo ($p=0.005$). A shorter medication course is easier for patients and would be preferred if the clinical effect was the same, and a completed study at OHSU utilized a seven-day course. Therefore, we are also studying a seven-day course of tamoxifen, administered 10mg twice daily.

Study follow up: In prior similar studies, subjects recorded prospective daily bleeding diaries for 90 days following enrollment and receive multiple doses of study medication. This study will only follow patients prospectively for 30 days following one drug administration. It was felt that extending the duration of subject involvement to three months would be prohibitive for recruitment and for completion of the study within the desired time frame. Subsequent studies can expand on the results of this initial study if tamoxifen is found to be beneficial.

1.3.13 Duration of project

We anticipate that it will require approximately 6 months to complete enrollment, and hope to begin enrollment in May, 2016. We aim to complete enrollment by October, 2016, with the last subject finishing her study period by November, 2016. Data analysis and write-up will continue through late 2017. Total duration of the project is anticipated to be approximately 15 months.

1.5 Links with other projects

This study is not linked to other projects.

1.6 Main problems anticipated

Recruitment: The family planning clinic at OHSU provides insertion of approximately 3-5 LNG-IUS devices per week. Additional insertions occur in the resident and generalist clinics. By targeting eligible women at clinic visits and by minimizing follow up procedures, we anticipate that recruitment will be feasible to complete within six months.

Retention: The short duration of the study and minimal follow up procedures should maximize retention. Similar prior studies in the LNG-IUS had low dropout rates, all with <20% loss to follow up (16,26,27). The proposed project is shorter duration (51 days total), which should decrease dropout even further. Nevertheless, our sample size was designed to account for a 20% dropout rate due to this risk of poor retention in women experiencing ongoing bleeding. Details on how we will manage loss to follow up are included in section 1.3.7.

Bleeding diaries: The text or email message bleeding diary through Mir3 has been utilized in similar studies with excellent response rates. However, a portion of participants in older studies had difficulty receiving or responding to text messages due to incompatible cell phone technology. Subjects who have difficulty receiving or responding to daily text messages can opt to receive identical email study survey messages instead and will have a paper diary to use as backup, which will utilize the exact same question and response categories.

Any unanticipated problems will be addressed by the PI and study co-investigators, with changes to the protocol as needed. Unanticipated problems could include medication side

effects or pregnancy in a study subject. Any pregnancy occurring during the study will be considered a serious adverse event and will prompt review of the study protocol and possible study discontinuation of the study.

1.7 Expected outcomes of the study and dissemination of findings

We anticipate that tamoxifen taken preventively will reduce the total number of bleeding days by at least 40%. We anticipate that subjects using tamoxifen to manage bleeding will report higher satisfaction with their bleeding profiles and with the LNG-IUS, and that more women receiving tamoxifen will report their bleeding as acceptable. Overall, improvements in bleeding patterns will translate into better overall acceptability of this highly effective LARC, which should improve continuation and uptake. Increasing the uptake and continuation of LARCs such as the LNG-IUS will lead to a reduction in unplanned pregnancies, which is a major public health concern (1,9).

The results of this study will be submitted for publication in a journal specific to obstetrics and gynecology, and will be presented to the national family planning professional community at the annual Family Planning Fellowship meeting.

2. ETHICAL CONSIDERATIONS

The study will be reviewed by the OHSU Institutional Review Board.

2.1 Informed decision-making and confidentiality

See attached lay language summary and consent form for patients who are choosing to enroll in this study. The statement of privacy from Mir3 is also attached.

3. BUDGET

3.1 Line-Item Budget

Please see separate form

4. APPENDICES

Appendix A: Consent and authorization form

Appendix B: Text of bleeding diary and study medication text and email messages

Bleeding diary guide

(to be reviewed at the first visit, and given to each subject to take home)

Every day that you are in the study, you should receive two messages at about 8pm. The first message will ask about your bleeding. You should respond with the number that corresponds to your bleeding for that day.

You can choose:

1. Bleeding – any day when your bleeding requires the use of protection with a tampon, pad or panty liner. It can be light or heavy.
2. Spotting – Minimal bleeding that does not require the use of any protection. For example, spotting just on toilet paper.
3. No bleeding - If you wear a pantyliner “just in case,” but don’t have bleeding, choose this response.

The second message will ask if you took the study drug on that day.

You can choose:

1. Yes
2. No

When you fill out the paper diary, please use this same code.

Text of the text messages sent each day by Mir3:

Over the past 24 hours, have you experienced:

1. Bleeding
2. Spotting
3. No bleeding or spotting

Did you take the study drug today?

1. Yes
2. No

Text of the email messages sent each day by Mir3:

Email subject line: Bleeding survey issued at (date) 8:00 PM

Over the past 24 hours, have you experienced:

You may respond by doing one of the following:

- Call [name] and use Telephony ID 628329179
- Select one of the responses below by clicking on the desired Response text.
- Reply to this email with the corresponding number to your response on the top line within the body of the email, e.g., 1 for indicating that you wish to use response option 1.

Option# Response:

1. Bleeding
2. Spotting
3. No bleeding or spotting

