A second message will be sent one minute after the first to inquire whether subjects took the study medication that day. If the subject does not respond to the text or email messages, a second set of texts or emails (2) will be sent the following morning. The subject has only these two chances to report their bleeding information for that day, and otherwise must use the paper diary. Responses to the messaging system will be compiled in a secured web database by Mir3, which can be accessed by research staff for data retrieval and entry onto research computers. Paper diaries will also be provided for use in case of technical difficulty in receiving or responding to text or email messages. Subjects are encouraged to complete paper diaries in addition to the electronic diary.

Follow up visits

Thirty days after initiating study drug, participants will receive an email with a link to a final study online survey via REDCap (attached). This survey will include questions assessing side effects, adverse events, and bleeding and IUS satisfaction. The satisfaction questions will utilize an electronic 100-mm visual analog scale. This study survey should take approximately 5-10 minutes to complete. Subjects not returning the survey within 7 days will be contacted by phone, text or email (based on stated contact preferences) and reminded to reply.

Compensation

Subjects will be compensated \$10 at enrollment and \$30 at the first study visit, which totals \$40. Additionally, subjects will be provided with compensation for completing the electronic bleeding diaries after use of study drug. Subjects will receive an additional \$1 each day that they respond to the electronic messages (up to 30 days total) and \$20 for completing the final survey. This is a total of up to \$50 that they can earn from completing the diaries and completing the study. The total compensation per subject is a maximum of \$90. Compensation will be loaded onto a debit card, which participants will receive at the enrolment visit.

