Appendix B: Bleeding diary text

Email subject line Study medication survey issued at (date) 8:02 PM

Did you take the study drug today?

You may respond by doing one of the following:

- Call [name] and use Telephony ID 628329179
- Select one of the responses below by clicking on the desired Response text.
- Reply to this email with the corresponding number to your response on the top line within the body of the email, e.g., 1 for indicating that you wish to use response option 1.

Option# Response:

1. Yes
2. No

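### The text-message diary uses digits 1 and 2 for both the bleeding question and the drug question, so a drug reply stored under the wrong question could add a false bleeding/spotting day to the primary count

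*Combined protocol and SAP*

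**What the plan says.** Appendix B says of the daily contact: "Every day that you are in the study, you should receive two messages at about 8pm". For the first message the guide instructs: "You should respond with the number that corresponds to your bleeding for that day". Of the other it says: "The second message will ask if you took the study drug on that day". Section 1.3.7 gives the spacing: "A second message will be sent one minute after the first to inquire whether subjects took the study medication that day". It also provides for the pair to be sent again the next morning, but only when a woman has not responded.

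The text wording in Appendix B is:

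- "Over the past 24 hours, have you experienced": 1 = bleeding, 2 = spotting, 3 = neither.
- "Did you take the study drug today": 1 = yes, 2 = no.

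The email versions differ in form. Each question has its own subject line (for the drug question, "Email subject line Study medication survey issued at (date) 8:02 PM") and clickable options, so an email reply carries its question with it.

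Section 1.3.11 builds the primary outcome on these replies: "subjects will indicate via numeric coded text or email message response whether they had spotting, bleeding, or none". Bleeding and spotting days are then added together over the 30 days from the start of treatment.

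**The concern.** In text mode a woman answers two questions with bare digits, and 1 and 2 are valid answers to both. The documents do not say how a digit is assigned to a question, or what happens to a single reply, a reply out of order, or one that overwrites another.

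Both drug answers are also bleeding/spotting codes. A drug reply stored as the bleeding answer therefore scores a bleeding/spotting day whatever the truth. On the days without study drug, which are the run-in and about 30 − 7 = 23 of the 30 primary days, the truthful drug answer is 2, the spotting code. False days can arise only on bleeding-free days, and an effective drug produces more of those. At equal error rates the tamoxifen mean would rise more than the placebo mean, so the estimated effect would be pulled towards zero. The run-in count, which the plan may use as a covariate, is exposed in the same way.

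**Working it through.** **Inputs.** From section 1.3.2: placebo mean 18 days, SD 7, a 40% reduction (described as about 7 days), 80% power, alpha 0.05, 21 women per arm, 20% dropout. From section 1.3.11: two-sided t-test. The miscoding share q is not in the documents; I assume a range.

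**The plan's own figure.** For a 7-day difference and SD 7, the two-sided t-test needs 16.71 women per arm. 16.71 / 0.8 = 20.9, so 21 per arm and 42 in all. The stated sample size reproduces and is not in question here.

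**What each kind of misroute does to the primary count.**

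- Drug reply stored as the bleeding answer, bleeding-free day: one false bleeding/spotting day.
- Drug reply stored as the bleeding answer, true bleeding or spotting day: no change, because codes 1 and 2 are pooled.
- Bleeding reply stored as the drug answer, with no other reply: a missing bleeding day, not a false one.
- Both answers swapped on a bleeding-free day: a false day, but a 3 lands in the drug field, where it is invalid.

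**Effect on the contrast.** The planned means are 18 and 18 × 0.6 = 10.8, a difference of 7.2. They leave 12 and 19.2 bleeding-free days. If a share q of those days is miscoded equally in both arms:

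(18 + 12q) − (10.8 + 19.2q) = 7.2 × (1 − q)

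**Effect on power.** Expected completers are 21 × 0.8 = 16.8 per arm; I use 17. If errors are spread evenly over women, the miscoding also compresses the spread. The variance in an arm becomes (1 − q)² × 49 + q(1 − q) × (mean number of bleeding-free days), averaged over the two arms.

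| q | Placebo | Tamoxifen | Difference | Relative reduction | SD | Power |
|---|---|---|---|---|---|---|
| 0 | 18.00 | 10.80 | 7.20 | 40.0% | 7.00 | 82.8% |
| 2% | 18.24 | 11.18 | 7.06 | 38.7% | 6.88 | 82.6% |
| 5% | 18.60 | 11.76 | 6.84 | 36.8% | 6.71 | 82.2% |
| 10% | 19.20 | 12.72 | 6.48 | 33.8% | 6.41 | 81.5% |

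At q = 10%, for example, the variances are 39.69 + 1.08 = 40.77 and 39.69 + 1.73 = 41.42, so the SD is √41.09 = 6.41.

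**Clustered errors.** Suppose instead that 10% of women are affected and the rest are not. The variance is then that of a mixture of the two groups.

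- Affected on half their bleeding-free days: difference 6.84, SD 7.18, power 76.9%.
- Affected on all of them: difference 6.48, SD 8.20, power 60.9%.

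These have the same average q as the 5% and 10% rows above. The power loss comes from the added spread between women.

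**The case against.** The strongest reply is that shared digits do harm only if the system cannot tie a reply to its question, and nothing shows that it cannot. Section 1.3.7 describes a diary built for this study with a provider used before with good response rates, and the email templates treat the two questions as separate surveys. That stands: neither misrouting nor its frequency is demonstrated. But a response rate shows that women reply, not that replies reach the right field, and the documents do not describe text routing.

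A reader might infer that the errors could never be found. The documents do not support that. A full swap on a bleeding-free day leaves an invalid 3 in the drug field. Women are trained on the diary, diaries are reviewed at visit 1, and a co-investigator reviews bleeding and medication data monthly. A paper diary gives a second record. These checks are partial. One sentence of section 1.3.7 asks all women for the paper diary and another only encourages it, and no rule reconciles it with the electronic one. The outlier and data-entry checks in section 1.3.10 would not flag a legal 1 or 2. A lone or overwritten reply can look legal.

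A reader might also infer a material loss of power. Holding the SD at 7 gives 78.9% at q = 5% and 74.4% at q = 10%, but evenly spread miscoding also narrows the SD, and power then stays above 81%. A larger loss needs clustering, which is equally an assumption.

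Nor does every misroute inflate the count: some leave it unchanged and some produce a missing day. Four prompts open at once would arise only after a non-response, not routinely.

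**Conclusion.** The point holds as a design weakness in how the primary outcome is captured, not as a demonstrated error. The overlapping codes, the one-minute spacing and the lack of any stated link between a text digit and its question are on the page. A drug reply misfiled on a bleeding-free day can only add to the count.

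The firm consequence is attenuation of the estimate by the factor (1 − q) if miscoding is equal in both arms: a loss of 0.14 days at 2%, 0.36 at 5% and 0.72 at 10%. This is small at low q. Power is little affected by evenly spread errors and more affected by clustered ones. All of this rests on assumed values of q, on equal rates in both arms and on the plan's own means and SD. If the vendor already matches replies by message, q may be near zero. The change is worth making because it protects the primary count whichever way replies are routed.

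**What to change.** Before first enrolment:

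- Keep 1/2/3 for bleeding and give the drug question codes that do not overlap, for example Y/N. Use them consistently in the texts, emails, take-home guide and paper diary.
- Have the system re-ask any reply whose code does not belong to the question.

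A drug reply in the bleeding field, or the reverse, would then be an invalid value that can be caught at once. I would not go further and limit the primary count to replies that identify their own question. That could discard valid answers and create missing days for which the plan has no rule.

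The cost is a small wording change to Appendix B and the diary materials, plus a vendor configuration change. It needs no added visits or participants and leaves the analysis unchanged.
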